6.1.3. Missing data

As a general rule, missing data will not be imputed (i.e., missing data will not be replaced but will be handled as "missing" in the statistical evaluation), with the following exceptions for summary analyses:

Clinical safety laboratory variables given as "<xx" will be evaluated as 0.5*xx in the summary tables. In the listings they will be displayed as "<xx" or similar.

Data values below lower limit of quantification (LLOQ) or detection (LLOD) will be imputed with 0.5*LLOQ or 0.5*LLOD, respectively, for the analysis of continuous data. Values above the upper limit of quantification (ULOQ) or detection (ULOD) will be imputed with 2*ULOQ or 2*ULOD, respectively, for the analysis of continuous data. In the listings they will be displayed as "<xx" or ">yy" as appropriate. In the tables they will be displayed as "<LLOQ"/("<LLOD" or ">ULOQ"/(">ULOD" in descriptive statistics (e.g., in mean, median, min, max) as appropriate. A footnote will be added to show the value of LLOQ or LLOD or ULOQ or ULOD.

6.2. Subject dispositions

All potential rollover volunteers must enroll in this trial within less than 18 months of their last injection of a BNT162 candidate vaccine in the parent BNT162-01 or BNT162-04 trials.

Subjects of the BNT162-01 and BNT162-04 will undergo a full complete screening for this rollover trial. For example, screening clinical laboratory tests will be performed to assess the new baseline values for the BNT162-14 trial.

Depending on the timing of follow-up in the parent trial, data from the parent trial may be used to determine eligibility in this rollover trial after the trial subject has consented. Once the trial subject has enrolled into this rollover trial, all safety reporting will occur through this rollover trial, this includes the reporting of non-vaccine related AEs that are unresolved from the parent trial, SAEs, and adverse events of special interest. All events occurred earlier (within screening) will be captured into the parent trial databases. All events that occurred between the trials will be captured as medical history events. For subjects who receive a non-trial SARS-CoV-2 vaccination, events will be collected until the date when the subject was vaccinated with the non-trial SARS-CoV-2 vaccine.

For the SCR, a listing of subjects having failed screening for BNT162-14 will be presented. This listing will include subjects having failed first screening and, if applicable, re-screening.

Subject disposition will be listed with date of informed consent, date of screening, date of injection and date of trial completion/discontinuation.

The number and percentage of subjects in the analysis sets will be summarized for the subjects in the SAF.

For the SAF, number and percentage of subjects having prematurely discontinued the trial with a summary of the primary reason (e.g., adverse events, death, withdrawal by subject, lost to follow-up) and of subjects who completed the trial will be presented.

Subjects having prematurely discontinued will be listed with date and reason for premature discontinuation.

Subjects in the SCR but excluded from the SAF, subjects in the SAF but excluded from the SAFB/IMM/IMMPP will be listed with reason for exclusion.

6.3. Baseline characteristics

6.3.1. Demographics

Demographic and baseline variables will be summarized for subjects in the SAF analysis set. Age (calculated as age [years] + age_months [months] /12) and weight [kg] will be summarized as continuous data.

Additionally, age will be summarized with the following categories:

• 18 to <= 64 years

- 65 to <= 84 years
- >=85 years

Gender (male or female), ethnicity (Hispanic or Latino, Not Hispanic or Latino, Not reported, Unknown), race (White, Black, or African American, Asian, American Indian or Alaska Native, Native Hawaiian or Other Pacific Islander, Not reported, Unknown, Other) and country will be summarized as categorical data.

A listing of demographic data will be provided.

6.3.2. Concomitant medication

For Group A, prior and concomitant medications will be defined using start and stop dates recorded, relative to the first and last injection of trial medication. Any medication taken before 28 days prior to the start date of IMP injection will not be classified as prior or concomitant medication unless a SARS-CoV-2 vaccination was received outside of the parent trial (outside the booster phase). A prior medication will be defined as any therapy taken 28 days prior to (but not including) the start date of IMP injection. A concomitant medication will be defined as any medication either:

- Taken prior to (but not including) the start date of IMP injection and
 - Ongoing at the first vaccination
 - Or with a missing end date
- Or with a start date on or after the date of the first injection (Dose 1) up to Visit 4 (Group A and Immunology subset of Group B) or up to Visit 10 (Immunology subset of Group B transplant subjects)
- Or with a start date on or after the date of the first injection (Dose 1) until the last trial visit for any non-trial SARS-CoV-2 vaccinations

If a medication cannot be clearly assigned to prior medication due to missing dates, it will be evaluated as concomitant medication.

Medications will be coded using the WHO Global (Drug Insight) March 2021 B3 standard drug codes resulting in Anatomical Therapeutic Chemical (ATC) codes indicating therapeutic classification. This also includes COVID-19 vaccine adaptations in WHO Global (Drug insight) March 2021.

Listings of prior and concomitant medications will be provided.

Concomitant therapy recording is not required for Group B but will be recorded in the SAE or AESI report.

6.3.3. Medical history

Medical history data will be coded using the Version Medical Dictionary for Regulatory Activities (MedDRA[®]) coding system 24.0.

A summary table of type of transplant and number of transplants will be provided for the transplant subjects.

A listing of medical history data will be provided. A listing of transplant information and HIV information will be provided.

6.4. Primary endpoint analyses

The primary endpoints are solicited local reactions at the injection site occurring up to 7 days after each injection, solicited systemic reactions occurring up to 7 days after each injection, the proportion of subjects with at least one serious adverse event (SAE) occurring up to 26 weeks after the first injection, the proportion of subjects with at least one adverse event of special interest (AESI) occurring up to 26 weeks after the first injection and the proportion of subjects with at least one unsolicited treatment emergent adverse event (TEAE) occurring up to 28 days after each injection.

All primary analyses will be performed using the SAF and analyses of adverse events for Group B will possibly be repeated using the SAFB.

6.4.1. Solicited local reactions

Definition

Solicited local reactions at the injection site consist of pain, tenderness, erythema/redness, and induration/swelling. These are assessed by the subject in a diary as stated in the protocol Section 8.2.4.

Local reactions will be graded based on the criteria given in the United States (US)Food and Drug Administration (FDA) Guidance for Industry 'Toxicity Grading Scale for Healthy Adult and Adolescent Volunteers Enrolled in Preventive Vaccine Clinical Trials' for 'Local Reaction to Injectable Products'. The grading of local reactions to injectable product is detailed in Section 10.3.2.1 (Table 5) of the protocol. The grades are Grade 1 (mild), Grade 2 (moderate), Grade 3 (severe), and Grade 4 (potentially life threatening).

The solicited local reactions will be evaluated for each injection, i.e.

- First injection (Dose 1) up to day 7 (inclusive) after first injection (Group A, immunology subset of Group B)
- Second injection (Dose 2) up to day 7 (inclusive) after second injection (Dose 2) (immunology subset of Group B)
- Both intervals combined (immunology subset of Group B)

The intervals will start with the date and time of the injection.

Note: The interval 'first injection (Dose 1) up to day 7 after first injection (Dose 1)' includes study day 1 to study day 7. This applies to the other intervals accordingly.

All analyses are based on local reactions independent of their relatedness to IMP.

Analysis

All analyses will only be performed for Group A and immunology subset of Group B.

Local reactions with missing time and occurring on the day of first injection (Dose 1) will be assigned to all intervals starting with the first injection (Dose 1). Local reactions with missing time and occurring on the day of the second injection (Dose 2) will be assigned

to all intervals including the second injection. Local reactions with missing date will be assigned to each of the applicable intervals if it cannot be ruled out, that it belongs to the time interval.

The number and percentage of subjects reporting at least one local reaction in each applicable time interval will be summarized for any local reaction and by worst grade.

The denominator of the percentages will be the number of subjects with any information on local reactions in the diary available in the respective time interval.

The number and percentage of subjects reporting at least one local reaction will be summarized by local reaction type (pain, tenderness, erythema/redness, and induration/swelling) and by worst grade for each time interval. The denominator of the percentages will be the number of subjects with any information on local reactions in the diary available in the respective time interval. This analysis will be repeated for local reactions of Grade \geq 3.

Additionally, the following analyses will be done for local reactions and for any reaction (local or systemic):

Time after first injection (Dose 1) (Group A and immunology subset of Group B) and after second injection (Dose 2) (immunology subset of Group B) from

- First injection (Dose 1) to first reaction
- First injection (Dose 1) to first reaction of Grade ≥3
- First reaction to last reaction and
- First reaction of Grade \geq 3 to last reaction of Grade \geq 3

will be determined per subject and will be summarized descriptively overall and by local reaction term.

Moreover, the frequency of subjects with any solicited local reactions and solicited reactions within 7 days after each dose per day and the frequency of subjects with solicited local reactions within 7 days after each dose by term per day will be analyzed. This analysis will be analyzed additionally for solicited local reactions of Grade \geq 3.

The compliance with the diary from each injection up to 7 days after each injection will be presented. A table giving the number and percentage of subjects with any information on local reactions in the diary (overall and by local reaction term) available per day will be given. The compliance with the diary based on any information on any reaction (local or systemic) will also be given.

All local reactions from the trial will be listed. Additionally, all days with information on local reactions in the diary will be listed.

For Group A (by randomization) and immunology subset of Group B (by transplant status yes/no), local reactions assessed by subject will be presented graphically using a bar plot. The following plot will be provided:

• Local reactions within 7 days after each dose by worst grade

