1.3 Schedule of activities

The SoAs provide an overview of the protocol visits and procedures. The investigator may schedule visits (unplanned visits) in addition to those listed in the SoAs, in order to conduct evaluations or assessments required to protect the wellbeing of the trial subjects.

Activity		Visit 0	Visit 1	Visit 2	Visit 4	Visit 5	Visit 6 ^k	Visit 7 ^k	Early termination
W	eek(s)			1	4	7	12	26	
	Day	-30 to -1	1	8+2	29±7	50±7	85±10	182±20	
		(Screening)	(Day of inj. 1; pre-dose except IMP injection)	(~7 d post inj.)	(~28 d post inj.)	(~49 d post inj.)	(~84 d post inj.)	(~181 d post inj. EOT Visit)	
Collect informed consent		Х							
Assess inclusion/exclusion criteria compliance		Х	X (review)						
Collect demographic and medical history		Х	X (update)						
Physical examination		Х	X a	X a	X a			X a	X a
Vital signs, body weight ^b		Х	Хc	Х	Х			х	Х
Urine pregnancy test for WOCBP		Х	х					х	х
Urine for clinical laboratory ^d		Х	х		Х			х	х
Blood draws for clinical laboratory (15 mL) ^e		Х	х		Х			х	Х
Allocation and randomization to IMP			х						
IMP injection, then observe subjects for ~1 h			х						
Subject hotline availability		Start	=>	=>	=>	=>	=>	End	(End)
Oral swabs for NAAT-based SARS-CoV-2 for screen	ing ^f	Xg	X a						
Oral swabs for NAAT-based SARS-CoV-2 for surveill	ance			Х	Х	Х	Х	х	х
Oral swabs for SARS-CoV-2 sequencing ^h		Xg	Хa	Х	Х	Х	Х	х	х

Table 1: Schedule of events for Group A (with one injection of either Comirnaty or BNT162b2s01)

Activity	Visit 0	Visit 1	Visit 2	Visit 4	Visit 5	Visit 6 ^k	Visit 7 ^k	Early termination
Week(s)			1	4	7	12	26	
Day	-30 to -1	1	8+2	29±7	50±7	85±10	182±20	
	(Screening)	(Day of inj. 1; pre-dose except IMP injection)	(~7 d post inj.)	(~28 d post inj.)	(~49 d post inj.)	(~84 d post inj.)	(~181 d post inj. EOT Visit)	
Blood draws for NATAB and nucleocapsid protein testing (15 mL)		х	х	Х		Х	х	х
Blood draws for CMI (120 mL each)		Х	Х			Х	х	Х
Issue/collect subject diaries		X (issue)	X (collect)					
Subjects report daily reactogenicity (incl. body temperature) in their diary on Day 1 and for 7 d post each vaccination		X (post- dose) ^j	х					
Record AEs since last visit		х	Х	Х	Xi	Xi	Xi	X ⁱ
Record pregnancies		Start	=>	=>	=>	=>	End	(End)
Record concomitant medication		Х	Х	Х	XI	XI	XI	XI

Note: The SoA allows for ad hoc SARS-CoV-2 testing for symptomatic or asymptomatic subjects.

a Brief (symptom-directed) physical examination; no height measurement.

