3 OBJECTIVES AND ENDPOINTS

OBJECTIVES	ENDPOINTS	
Primary objectives	Endpoints	
To determine the safety and tolerability of one or two boosting doses of Comirnaty or one dose of BNT162b2s01 in BNT162-01 trial subjects, or two boosting doses of Comirnaty in BNT162-04 trial subjects.	 For all Group A and Group B subjects: The proportion of subjects in each treatment group with at least one SAE or the proportion of AESIs occurring up to 26 weeks after the first IMP injection. For Group A and a selected subset of Group B subjects: The frequency of solicited local reactions (pain, tenderness, erythema/redness, induration/swelling) at the injection site recorded up to 7 d after each IMP injection. The frequency of solicited systemic reactions (vomiting, diarrhea, headache, fatigue/tiredness, fever, chills, nausea, new or worsened muscle pain, new or worsening joint pain) recorded up to 7 d after each IMP injection. The proportion of subjects with at least one unsolicited TEAE occurring up to 28 d after IMP injection in each treatment group. 	
Secondary objectives	Endpoints	
To describe changes in SARS-CoV-2 neutralizing antibody titers from baseline to reference and SARS-CoV-2 variant B.1.351.	 For Group A and Group B subjects (except transplant subjects): Antibody titers to recombinant S1 and RBD protein derived from reference and SARS-CoV-2 variant B.1.351** will be assessed at baseline (Day 1) and then Day 8, Weeks 3*, 4, 7*, 12, and 26: Neutralizing antibody titers. Antibody titers (ELISA). SARS-CoV-2 functional cross-neutralization of variant B.1.351** to reference strain. *Group B only **Group B transplant subjects only: Antibody titers to recombinant S1 and RBD protein derived from SARS-CoV-2 will be assessed at baseline (Day 1) and then Day 8, Weeks 4, 12, and 26 post Dose 1, and at Dose 2 (Day 1) and then Day 8, Weeks 4, 12, and 26 post Dose 2: Neutralizing antibody titers. Antibody titers (ELISA). 	
Exploratory objectives	Endpoints	

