9.4.2 Primary endpoints

The primary endpoints are defined in Section 3.

All AEs will be coded using the most recent version of Medical Dictionary for Regulatory Activities (MedDRA[®]) coding system to get a system organ class (SOC) and preferred term (PT) for each AE.

Reactogenicity

Solicited local and systemic reactions (from the subject diary) will be summarized using the Safety Set. In general, solicited reactions will be analyzed for each immunization, i.e.:

• Up to 7 d after each IMP injection

For each injection, the number and percentage of subjects reporting at least one local reaction or systemic reaction (i.e., solicited data collected using subject diaries) will be summarized for each of the following types using the Safety Set:

BioNTech SE	Clinical Trial Protocol
Confidential	BNT162-14

- Any local reactions or systemic reactions
- Grade ≥3 local reactions or systemic reactions

Moreover, the number and percentage of subjects reporting at least one local reaction will be summarized by worst grade using the Safety Set.

Unsolicited TEAEs

For Group A and Group B immunology subset, the number and percentage of subjects reporting at least one TEAE (defined in Section 10.3.1) will be summarized by PT nested within SOC for each of the following AE types using the Safety Set:

- Any AE
- Related AE
- Grade of AE
- Related Grade ≥3 AE
- Any solicited AE that continues past 7 d post-trial injection or is an SAE, or AE that fits the definition of a solicited AE but starts after Day 8
- Any SAE
- Related SAE
- AESI

Moreover, the number and percentage of subjects with any AE will be summarized by worst grade by PT nested within SOC.

For Group B, AESIs and SAEs will be analyzed.

Additional AE analyses may be described in the SAP.

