6.1.2. Definitions and derivations

Unscheduled visits

Unscheduled visits will not be included in the summary tables but will be included in the listings.

Variables

Unless otherwise specified, **baseline** is defined as last value prior to first injection of IMP (Dose 1) given in this BNT162-14 trial on Day 1, including unscheduled visits.

Change from baseline will be calculated as follows:

• Change from baseline = post-baseline assessment value – baseline assessment value.

Duration [days] will be calculated as follows:

• Duration [days] = last observation date – first observation date + 1

Time from first injection (Dose 1) to first reaction will be calculated as follows: Time from first injection to first reaction [days] = first reaction date – date of first injection (Dose 1) + 1

Time from first reaction to last reaction will be calculated as follows:

Time from first to last reaction [days] = last reaction date – first reaction date + 1

Days since last injection will be calculated as follows:

Days since last injection = onset date of AE – date of last injection +1

For conversion of days to months or years the following rules will be applied:

- 1 month = 30.25 days
- 1 year = 365.25 days

Study Day and are defined as follows:

- Study day:
 - If study date < date of first injection (Dose 1), then study day = study date date of first injection
 - If study date >= date of first injection (Dose 1), then study day = study date date of first injection + 1

Fold rise will be calculated as follows:

• Fold rise = post-dose value / baseline value

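### The SAP contradicts itself on the solicited-reaction window (Day 7 or Day 8, counting the injection as Day 1), and its Dose 2 time-to-reaction summary has no Dose 2 origin

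*SAP*

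**What the plan says.** **Endpoint.** Protocol section 3 defines the frequency of solicited local reactions "at the injection site recorded up to 7 d after each IMP injection" and words the systemic endpoint the same way. Protocol 9.4.2 gives the analysis period as "Up to 7 d after each IMP injection". SAP 6.4 restates the endpoint as "solicited local reactions at the injection site occurring up to 7 days after each injection".

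**Interval.** The first interval bullet in SAP 6.4.1 reads "First injection (Dose 1) up to day 7 (inclusive) after first injection". The Note below it then says the interval "includes study day 1 to study day 7. This applies to the other intervals accordingly". SAP 6.4.2 has the same bullets and Note for systemic reactions and takes over the 6.4.1 analyses by reference.

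**Day count.** In SAP 6.1.2 the rule that opens "If study date >= date of first injection (Dose 1), then study day" gives the date difference plus one. Study day is defined from Dose 1 only.

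**Diary.** Group A subjects report "in their diary on Day 1 and for 7 d post each vaccination" (protocol 1.3, Table 1). Tables 2 and 2a ask for seven days after each vaccination without naming Day 1 separately. Protocol 8.2.5 has subjects assess reactions daily until 7 d after each injection.

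**Time to reaction.** SAP 6.4.1 introduces these summaries as covering both doses. Both to-first-reaction bullets (any grade, and Grade 3 or higher) nevertheless begin at the first injection, and the one formula in 6.1.2 subtracts the Dose 1 date.

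**Declared changes.** SAP Appendix 1 lists a single change, about AE grades. It does not mention the diary window.

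**The concern.** A programmer who meets a general bullet followed by an explicit Note will probably code the Note. The interval and worst-grade tables for a primary endpoint would then stop one day before the endpoint does, with no record that this was intended.

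Other outputs are described differently. The daily frequency table covers "any solicited local reactions and solicited reactions within 7 days after each dose per day", and the compliance table and bar plots use similar wording. Whether the Note governs them is unclear, so outputs on the same endpoint might end on different days. For Dose 2 the Note cannot be applied as written, because no study day is counted from Dose 2.

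The timing problem is separate. Coded literally, the Dose 2 onset summary would report the gap between doses plus the reaction time, which describes the dosing schedule and not the vaccine.

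**Working it through.** **1. Check the day count.** By SAP 6.1.2, study day = date − Dose 1 date + 1, so days after injection = study day − 1. This reproduces the visit labels in protocol Table 1: Day 8 → 7 d, Day 29 → 28 d, Day 50 → 49 d, Day 85 → 84 d, Day 182 → 181 d. The two documents count days in the same way.

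**2. Apply it to the window.**
- Note: study Day 7 → 7 − 1 = 6 days after injection; 7 calendar days covered.
- Endpoint: 7 days after injection → study Day 7 + 1 = 8; 8 calendar days covered.
- Dose 2 at the nominal Day 22: endpoint window Days 22 to 22 + 7 = 29; the Note by analogy gives Days 22 to 22 + 6 = 28.

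Counting the injection day as the first of seven days would give Day 7. That does not fit the SAP bullet (inclusive of day 7 *after* injection), the Group A diary wording, or the Day 8 visit labelled about 7 d after injection.

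**3. Follow a non-serious diary reaction through the rules** (days counted from the injection, Note applied):

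| Reaction | Interval tables | AE form |
|---|---|---|
| Starts by Day 7, first reaches worst grade on Day 8, ends Day 8 | Counted, at a lower grade | No |
| Starts and ends on Day 8 | Not counted | No |
| Starts on Day 8, lasts beyond it | Not counted | Yes by protocol 8.2.4; not covered by the wording of protocol 8.3 and SAP 6.4.3 |
| Starts before Day 8, lasts beyond it | Counted, graded on Days 1 to 7 | Yes |

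All of these remain in the SAP's listings of reactions. What is missing from both the interval tables and the AE form is mainly the second row; the first row's Day 8 worst grade is missing too.

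**4. Dose 2 time to first reaction.** The SAP formula is first reaction date − Dose 1 date + 1. For a reaction on the day of Dose 2:
- Non-transplant, Visit 3 at Day 22 ± 3: 22 days nominally, 19 to 25 over the visit window.
- Transplant, Dose 2 at 3 to 7 months, with the SAP's 30.25 days per month: 3 × 30.25 + 1 = 91.75 to 7 × 30.25 + 1 = 212.75, or about 92 to 213 days.
- Counted from Dose 2: 0 + 1 = 1 day in both groups.

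The non-transplant range assumes no delay. Protocol 7.1.2 permits delays to Dose 2, which would lengthen it. The dosing tables put Dose 2 at Day 21 and the schedule at Day 22 ± 3; those passages must be reconciled, and Day 21 would lower the nominal figure to 21.

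**The case against.** - **A seven-entry diary on Days 1 to 7 is a legitimate design, and arguably the more complete one.** Protocol 8.2 asks for evening entries until the day of the next visit, and the diary is collected at Visit 2 (Day 8+2). A subject seen on Day 8 may hand it in before a Day 8 evening entry exists, whereas Days 1 to 7 can be completed by every on-schedule subject after Dose 1. This stands. It is a good reason to allow a declared Days 1 to 7 window and to report Day 8 completeness, but not to leave the departure undeclared.
- **The Dose 2 intent is clear from the introductory sentence.** This also stands: it is a drafting slip, and the long times arise only if the bullets and formula are followed literally. They are, however, the only derivation given.
- **Nothing is tested.** There is no formal hypothesis and the outputs are descriptive. That limits the consequences but does not decide which day the primary tables end on.

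Three stronger readings are tempting and are not supported:
- *The SAP has settled on a short window.* It has not: its bullets and section 6.4 still state the full 7 days after injection, so this is a contradiction.
- *Day 8 reactions vanish.* They stay in the listings, and protocol 8.2.4 captures those that last beyond Day 8.
- *The daily and compliance tables will disagree with the interval tables.* They may, but they sit in the same section as the Note, and the SAP does not say whether it governs them.

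**Conclusion.** The point holds as an internal contradiction on a primary endpoint, together with a missing origin for a supporting summary. The Note ends the interval 6 days after injection where the endpoint says 7, leaving out one of eight calendar days.

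The effect on reaction rates is probably small. Protocol 2.3.1 describes reactions as usually resolving within a few days, but neither document gives reactions by day of onset, so no figure can be computed. A reader might infer materially understated reactogenicity; the documents give no basis for that.

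The Dose 2 timing error is large in value if coded as written (about 22 days, or 92 to 213 days, against 1), but it affects only a descriptive output. Both conclusions rest on the SAP's day count and on literal programming of the Note, bullets and formula. Correction is worthwhile before the tables are programmed; the trial's conclusions are not in doubt because of it.

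**What to change.** Change the SAP only:

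1. **Window.** Define the interval after each injection as the injection date through the injection date + 7, that is Days 1 to 8 counted from that injection, and amend the Note in 6.4.1 and 6.4.2. Report how many subjects have a Day 8 entry after each dose. The denominator accepts any diary information in the interval, so a missing last day would otherwise be invisible. If Days 1 to 7 is what was meant, declare it in Appendix 1 as a change from the protocol.
2. **Consistency.** Use the chosen dose-relative window in the interval, per-day, compliance and plot outputs. Align the Day 8 boundary in 6.4.3 with it, and state that it counts from the most recent injection, so that a Day 8 onset has a defined place.
3. **Dose 2 timing.** Define time to first reaction after Dose 2 (any, and Grade 3 or higher) as first reaction date after Dose 2 − Dose 2 date + 1, and correct the 6.4.1 bullets; 6.4.2 follows by reference.

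The cost is SAP wording and derivations on diary and injection dates already collected, with no protocol amendment. Day 8 entries that were never made cannot be recovered, which is why their number should be shown.
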